5.2 Use of co-intervention (if applicable)

- No co-intervention is allowed during the study period.
- Concomitant medicinal products that are strong inhibitors of CYP3A4 (i.e. azoles, erytromycine, antiretroviral drugs, grapefruit juice) should be used with caution, and chronic use of concomitant medicinal products that are strong inducers of CYP3A4 (rifampicin, certain anti-epileptics, st. John's wort) should be avoided.

5.3 Escape medication (if applicable)

Not applicable

6. INVESTIGATIONAL PRODUCT

6.1 Name and description of investigational product(s)

Cabometyx 20/40/60 mg film-coated tablets. See chapter 1, 2 and 3 of the Summary of product characteristics for more information.

6.2 Summary of findings from non-clinical studies

In nonclinical toxicology studies of cabozantinib in rodents and non-rodents, histopathological changes associated with cabozantinib administration were observed in gastrointestinal (GI) tract, bone marrow, lymphoid tissues, kidney, adrenal, and reproductive tract tissues, and secondary changes were observed in bone and pancreas. Cabozantinib tested negative in bacterial and mammalian cell genotoxicity assays *in vitro*. In reproductive toxicity studies, cabozantinib was embryotoxic in rats, produced fetal soft tissue changes in rabbits, produced fetal external malformations in rats, and decreased fertility in male and female rats. The metabolite present at highest concentrations in humans administered cabozantinib, EXEL-1644, was negative in an *in vitro* bacterial genotoxicity bioassay and caused no systemic tissue toxicity in rats. In a 2-year rat carcinogenicity study, cabozantinib-related neoplastic findings consisted of an increased incidence of benign pheochromocytoma, alone or in combination with malignant pheochromocytoma/complex malignant pheochromocytoma of the adrenal medulla in both sexes. No clinical cases of pheochromocytoma have occurred to date. No carcinogenic signal was observed in a rasH2 transgenic mouse model following cabozantinib dosing for 26 weeks. See chapter 4 of the IB and paragraph 5.3 in the Summary of product characteristics for more information.

6.3 Summary of findings from clinical studies

17 clinical studies of cabozantinib for oncology indications including four Phase 1 studies, one Phase 1b/2 study, four Phase 2 studies, five Phase 3 studies (a placebo-controlled study in subjects with medullary thyroid cancer, two active-controlled studies in subjects with CRPC, one ongoing open-label, active-controlled study in subjects with renal cell carcinoma, and one ongoing and enrolling double-blinded placebo-controlled study in subjects with hepatocellular carcinoma, one ongoing and enrolling Phase 4 study in medullary thyroid cancer, one ongoing maintenance “roll-over” study, and one expanded access study (Table 5-1 in the IB) are done. In addition, there are eleven clinical pharmacology studies (Table 5-2 in the IB); nine were conducted in healthy subjects alone, one study was conducted that included healthy subjects and subjects with renal impairment, and one study was conducted that included healthy subjects and subjects with hepatic impairment. In addition to these company-sponsored clinical studies, twenty-nine externally-sponsored studies and seventeen National Cancer Institute -Cancer Therapy Evaluation Program (CTEP) trials have enrolled subjects in oncology indications. Study results are summarized in paragraph 5.5 of the IB and paragraph 5.1 of the Summary of product characteristics.

6.4 Summary of known and potential risks and benefits

Cabozantinib has a well known safety profile, with 2467 patients treated within a clinical trial. Adverse event experienced by $\geq 20\%$ of these patients are listed in table 1-1 of the

IB. Serious adverse events experienced by $\geq 1\%$ of these patients are listed in table 1-2 of the IB. Benefits of cabozantinib in other cancers are described in paragraph 5.5 of the IB.

6.5 Description and justification of route of administration and dosage

Cabozantinib tablets are meant to be taken orally only and not to be crushed for dissolving in liquid or administered through other routes including percutaneous endoscopic gastrostomy (PEG) tubes. Cabozantinib tablets should not be administered to subjects who do not have adequate swallowing capacity. Cabozantinib is meant to be taken without food (subjects should not eat for at least 2 hour before and at least 1 hour after taking cabozantinib) with a full glass (at least 240 ml) of water. If a dose is missed, the missed dose should not be taken less than 12 h before the next dose. Dosage is described in paragraph 5.1 of this protocol and table 1 in the Summary of product characteristics (page 4).

6.6 Dosages, dosage modifications and method of administration

Starting dose of cabometyx is 60 mg once daily (40 mg once daily in case of liver function disorders). Recommended dose modifications are described in paragraph 5.1 of this protocol and table 1 in the Summary of product characteristics (page 4). The trial medication will be stored at the trial pharmacy and can be ordered by filling in an AKF-form. Subsequently, the research nurse of the medical oncology department will hand the medication over to the patient on the outpatient department.

6.7 Preparation and labelling of Investigational Medicinal Product

Preparation and labeling of the commercially available medicinal product will be performed by the pharmacy department according to in-house SOP and IB.

6.8 Drug accountability

Drug accountability will be registered per patient and overall. For 'per patient drug accountability' a drug dispensing log will be used (see the attachment). In this log, drug dispensation and returned drugs will be registered. A drug accountability log will be used for an overview of all dispensed and returned drugs (see the attachment).

7. NON-INVESTIGATIONAL PRODUCT

Not applicable

8. METHODS

8.1 Study parameters/endpoints

8.1.1 Main study parameter/endpoint

- Assess the ORR
 - Response will be measured according to RECIST version 1.1.¹³
 - ORR is defined as the sum of the complete remissions plus partial responses.⁹
 - The best response will be used in each patient.
 - An independent endpoint review committee will be installed to verify responses.

8.2 Secondary study parameters/endpoints (if applicable)

- Assess the PFS
 - PFS is defined as time from study enrollment until disease progression or death.
 - Outcome will be scored as 'progressed' or 'censored' according to the FDA guidance for industry of clinical trial endpoints.⁹
- Assess the OS
 - OS is defined as time from study enrollment until date of death of any cause.
 - Analysis of OS will be done at the end of the study (study related follow-up will be until 3 years after start of treatment)
- Assess the DoR
 - DoR is defined as time from study enrollment until date of documented tumor progression or death
 - Only patients with a CR or PR will be included in the assessment of DoR.
- Assess the toxicity of cabozantinib in SGC patients
 - Toxicity will be scored according to NCI CTC common criteria v 4.0.
- Assess the QoL of SGC patients treated with cabozantinib
 - QoL will be assessed using the EORTC QLQ-C30, EORTC QLQ-H&N35, PSSHN and VAS questionnaires.
- Assess the response rate of patients with advanced SGC treated with cabozantinib by using continuous tumor shrinkage end-points, as was advocated by Billingham et al¹¹ and Wason et al.¹²
- ctDNA will be assessed to evaluate whether treatment response and disease progression can be predicted.

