8.4 Study procedures

In chapter 3 (study design) we describe which assessments will be done and when. Below we describe what this means for a patient who decides to participate: how many study related visits will be made, how much blood will be drawn, how much radiation will be used etcetera.

- Treatment
 - A patient will use Cabometyx tablets once daily for a maximum of 2 years
- OPD visits
 - A patient will visit the OPD at week 0 (baseline), 2, 4, 6, 8, 12, 16, 20, 24, 32, 40, 48, 56, 68, 80, 92, 104 if he/she is on treatment for the maximum duration of 2 years. This means 17 planned study related visits in 2 years.
- Laboratory tests
 - Blood will be drawn by venapuncture at every visit.
 - At every visit, the following blood will be drawn:
 - First tube is always discarded → 3 ml tube
 - Hematology → 3 ml EDTA tube
 - Biochemistry → 3 ml lithium-heparin tube
 - ctDNA → 3x 8.5 ml Roche cell free DNA tubes
 - total: 34.5 ml of blood per visit
- Urine analysis
 - A urine portion will be analyzed for protein/creatinine ratio before start of treatment, after 2 weeks, and when clinically indicated.
- ECG
 - An ECG will be made before start of treatment, after 2 weeks, and when clinically indicated.
- Imaging
 - A neck-, chest-, and abdominal CT scan will be made in week 0, 8, 16, 24, 32, 40, 48, 56, 68, 80, 92 and week 104 if a patient stay on treatment during the maximum of 2 years. So 12 CT-scans of approximately 15 mSv will be made, resulting in a yearly exposure of 90 mSv. Taking the terminal disease into account, this corresponds to a effective dose in healthy adults of 9 mSv, which is a moderate risk. In our opinion, this exposure is justified concerning the relevance of the study. See the radiation ethic form for further details.
- Questionnaires
 - Questionairres will be taken 7 times (at baseline, week 8, week 16, week 24, week 40, week 56 and at PD)
 - The follow questionnaires will be taken:
 - EORTC QLQ-C30: 30 questions
 - EORTC QLQ-H&N35: 35 questions
 - PSSHN¹⁶: 3 questions
 - VAS: 1 question
 - Total: 30+35+3+1=69 questions

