10. STATISTICAL ANALYSIS

10.1 Primary study parameter(s)

Following Simon's design (as described in section 4.4) for RECIST v1.1, the null hypothesis will be rejected if more than 2 responses out of 17 patients are observed; in that case the conclusion is that the drug should be further investigated. This design yields a type I error rate of 0.047 and power 0.81 when the true response rate is 0.25. A 95% CI for the overall response rate per RECIST v1.1 will be calculated using the binomial distribution. Next to this, responses (CR, PR, SD and PD) will be described using simple descriptive statistics.

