Treatment effect will be measured with CT-scans every 8 weeks using RECIST criteria. It is not possible to predict treatment effect reliable before the first evaluation CT scan. In this study, we will collect blood samples for ctDNA analysis. The ctDNA samples will be analyzed in order to establish whether disease response can be predicted before the first evaluation CT-scan using ctDNA.

j. Can effects be managed?

In general side effects can be managed by either supportive treatment and/or dose reductions. Specific management of side effects is described in paragraph 6.2 of the IB. If side effect occur, the Radboudumc has 24-hour facilities including a level 3 intensive care to manage side effects.

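### Duration of response is timed from enrollment, not from first documented response, so it repeats PFS in responders and overstates how long responses last

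*Combined protocol and SAP*

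**What the plan says.** Section 8.2 gives this definition: "DoR is defined as time from study enrollment until date of documented tumor progression or death". Section 2 (secondary objectives) has the same sentence. Section 8.2 then restricts the analysis set: "Only patients with a CR or PR will be included in the assessment of DoR".

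For PFS, section 8.2 says "PFS is defined as time from study enrollment until disease progression or death", with events and censoring assigned "according to the FDA guidance for industry of clinical trial endpoints". No censoring rule is given for DoR.

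On timing, section 8.4 states that a CT "scan will be made in week 0, 8, 16, 24, 32, 40, 48, 56, 68, 80, 92 and week 104", which agrees with the assessment table in section 3. The first scheduled on-treatment scan is therefore at week 8.

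Section 10.2 sets out analyses for PFS, OS, toxicity, quality of life and tumor shrinkage. It has no entry for DoR, and nothing elsewhere starts DoR at the response.

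**The concern.** A duration of response should measure how long a response lasts once it has been seen. With the clock starting at enrollment, it also includes the time the patient took to respond. A patient who progressed or died in that period without having responded would not be in the DoR set. For those who are in it, the pre-response interval cannot contain an event, and counting it adds guaranteed event-free time to every value.

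This has three consequences:

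- The figure is biased upward in every responder.
- It carries no information beyond PFS in the same patients, although the protocol lists the two as separate objectives.
- Readers who take DoR to mean time in response would set it beside figures from other studies that do not measure the same thing.

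Each cohort will have few responders. At the 25% alternative, 17 × 0.25 = 4.25 are expected. With so few, the length of each response is a natural companion to the response rate.

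**Working it through.** The plan states no numerical DoR, so there is no figure of its own to reproduce. The check compares the definitions and then applies them to the plan's scan calendar.

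**Inputs.** The DoR definition (sections 2 and 8.2), the PFS definition and the responder restriction (section 8.2), and scans at weeks 0, 8, 16, 24, 32, 40, 48, 56, 68, 80, 92 and 104 (sections 3 and 8.4).

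**Step 1: definitions side by side.** Let E be enrollment, R the first documented CR or PR, and T progression or death.

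- PFS = T − E
- DoR as written = T − E, in responders
- DoR from first response = T − R

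In a responder, DoR as written minus PFS is (T − E) − (T − E) = 0. DoR as written minus DoR from response is (T − E) − (T − R) = R − E, the whole time to response.

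**Step 2: smallest excess on scheduled scans.** With E at week 0 and R no earlier than week 8, R − E is at least 8 weeks. That is 56 days, or 56 / 30.44 = 1.84 months. Section 8.6 provides for withdrawal before treatment starts, so enrollment can precede the first dose. Any such gap adds to the excess.

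**Step 3: relative excess.** Taking E = 0, this is R / (T − R). The response and progression weeks below are assumed, to show the range on the plan's calendar.

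| First response (week) | Progression (week) | DoR as written (weeks) | DoR from response (weeks) | Relative excess |
|---|---|---|---|---|
| 8 | 16 | 16 | 8 | +100% |
| 8 | 32 | 32 | 24 | +33% |
| 8 | 48 | 48 | 40 | +20% |
| 8 | 104 | 104 | 96 | +8% |
| 16 | 32 | 32 | 16 | +100% |
| 16 | 56 | 56 | 40 | +40% |
| 16 | 104 | 104 | 88 | +18% |
| 24 | 40 | 40 | 16 | +150% |
| 24 | 48 | 48 | 24 | +100% |
| 24 | 104 | 104 | 80 | +30% |

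For example, response at week 16 and progression at week 32 gives 16 / (32 − 16) = 100%. In absolute terms the excess depends only on when the response is first seen. In relative terms it is largest for late or short responses and smallest for early, durable ones.

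**Step 4: what is not affected.** Section 10.1 says "This design yields a type I error rate of 0.047 and power 0.81 when the true response rate is 0.25". The rejection probability is the sum over x = 1 to 9 of P(X₁ = x) × P(X₂ ≥ 3 − x), with X₁ ~ Bin(9, p) and X₂ ~ Bin(8, p). It is 0.0466 at p = 0.05 and 0.812 at p = 0.25, so both stated figures reproduce. Neither depends on DoR.

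**The case against.** The strongest reply concerns importance. DoR is an untested secondary endpoint with no threshold and no part in the sample size. Sections 4.4, 10.1 and 10.4 base both the stage 1 decision and the final conclusion on response counts alone. The historical comparisons in section 10.2 are for PFS and OS only, so no planned comparison uses DoR. The dates needed to recalculate it will be collected anyway, so nothing is lost for good. All of this stands. Any weight DoR would carry in a decision on further study is a reader's judgement, not something the plan assigns.

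Three qualifications on size also stand:

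- The 8-week minimum assumes scheduled scans. Section 3 allows other diagnostic procedures at the investigator's discretion, and an earlier scan would shorten the excess without removing it.
- Exact equality with PFS assumes the same censoring. The plan states a rule for PFS only and no different one for DoR.
- The number of responders is uncertain. At the 5% null, 17 × 0.05 = 0.85 are expected, and a cohort stopped with no responses has no DoR to report.

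The identical wording in sections 2 and 8.2 may be one drafting slip copied across. It is still the operative definition in both places. None of these points supplies a passage that starts DoR at the response.

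**Conclusion.** The concern holds. As defined, DoR does not measure how long responses last. It is the PFS interval in responders, and it exceeds time in response by each patient's whole time to first documented response. On scheduled scans, with enrollment at or before week 0, the excess is at least 8 weeks. Among the illustrative dates tabulated, the relative excess runs from +8% to +150%. The error always lengthens the reported figure. It is confined to this secondary objective and leaves the primary endpoint, the interim rule and the sample size untouched.

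**What to change.** In sections 2 and 8.2, define DoR as the time from the first scan documenting CR or PR, as verified by the endpoint review committee, to documented progression or death from any cause, in responders. State that the PFS censoring rules apply to DoR.

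In section 10.2, add a DoR line: a Kaplan-Meier estimate in responders for the SDC and ACC cohorts, and individual values for the third cohort, in keeping with how that section already handles its PFS and survival. Report time to response separately, so that the interval now hidden in DoR is still visible.

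The cost is one sentence in each of two sections and a line in section 10.2. No extra visit, scan or patient is needed. The reported DoR will be shorter. Making the change before the analysis avoids a post hoc redefinition.

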8.2.1 Other study parameters (if applicable)

- History
 - Birth date
 - Gender
 - General medical history
 - Medication use
 - Allergies
 - SGC history: diagnosis date, location primary tumor, TNM stage at diagnosis, ex-PA?, AR-status, HER2-status, type of surgery, date of surgery, postoperative radiotherapy, date of radiotherapy, adjuvant systemic therapy, location of recurrence, date of recurrence, palliative treatments
- Clinical examination:
 - Vital signs
 - Body weight
- Laboratory tests: Hematology, biochemistry, urine (see assessments)
- ECG: QT time, abnormalities

8.3 Randomisation, blinding and treatment allocation

This is a single arm study, so randomisation, blinding and treatment allocation are not applicable.

8.4 Study procedures

In chapter 3 (study design) we describe which assessments will be done and when. Below we describe what this means for a patient who decides to participate: how many study related visits will be made, how much blood will be drawn, how much radiation will be used etcetera.

- Treatment
 - A patient will use Cabometyx tablets once daily for a maximum of 2 years
- OPD visits
 - A patient will visit the OPD at week 0 (baseline), 2, 4, 6, 8, 12, 16, 20, 24, 32, 40, 48, 56, 68, 80, 92, 104 if he/she is on treatment for the maximum duration of 2 years. This means 17 planned study related visits in 2 years.
- Laboratory tests
 - Blood will be drawn by venapuncture at every visit.
 - At every visit, the following blood will be drawn:
 - First tube is always discarded → 3 ml tube
 - Hematology → 3 ml EDTA tube
 - Biochemistry → 3 ml lithium-heparin tube
 - ctDNA → 3x 8.5 ml Roche cell free DNA tubes
 - total: 34.5 ml of blood per visit
- Urine analysis
 - A urine portion will be analyzed for protein/creatinine ratio before start of treatment, after 2 weeks, and when clinically indicated.
- ECG
 - An ECG will be made before start of treatment, after 2 weeks, and when clinically indicated.
- Imaging
 - A neck-, chest-, and abdominal CT scan will be made in week 0, 8, 16, 24, 32, 40, 48, 56, 68, 80, 92 and week 104 if a patient stay on treatment during the maximum of 2 years. So 12 CT-scans of approximately 15 mSv will be made, resulting in a yearly exposure of 90 mSv. Taking the terminal disease into account, this corresponds to a effective dose in healthy adults of 9 mSv, which is a moderate risk. In our opinion, this exposure is justified concerning the relevance of the study. See the radiation ethic form for further details.
- Questionnaires
 - Questionairres will be taken 7 times (at baseline, week 8, week 16, week 24, week 40, week 56 and at PD)
 - The follow questionnaires will be taken:
 - EORTC QLQ-C30: 30 questions
 - EORTC QLQ-H&N35: 35 questions
 - PSSHN¹⁶: 3 questions
 - VAS: 1 question
 - Total: 30+35+3+1=69 questions

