2. OBJECTIVES

Objectives will be analyzed separately in all 3 cohorts of c-MET positive, advanced SGC: (1) SDC, (2) ACC originated in the salivary glands or other sites of the body, (3) other SGC's

Primary Objective

- Assess the ORR. ORR is defined as the sum of the complete remissions plus partial responses.⁹ The best response will be used in each patient.

Secondary Objectives

- Assess the PFS. PFS will be defined as time from study enrollment until disease progression or death.
- Assess the OS. OS will be defined as time from study enrollment until date of death of any cause.
- Assess the DoR. DoR is defined as time from study enrollment until date of documented tumor progression or death
- Assess the toxicity of cabozantinib. Toxicity will be scored according to NCI CTC common criteria v 4.0.¹⁰
- Assess the QoL of patients treated with cabozantinib using EORTC questionnaires.
- Assess the response rate by using continuous tumor shrinkage end-points, as was advocated by Billingham et al¹¹ and Wason et al.¹²
- ctDNA will be assessed to evaluate whether response and disease progression can be predicted.

More details about the definitions and analysis of primary and secondary outcomes are described in chapter 8.1.

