5. TREATMENT OF SUBJECTS

5.1 Investigational product/treatment

Patients will use cabozantinib tablets (Cabometyx®) once daily until progressive disease, intolerable toxicity, or investigator and/or patient decision to withdraw for a maximum duration of 2 years.

- Starting dose
 - 60 mg once daily
 - Liver function disorder: 40 mg once daily
 - Renal impairment: Cabozantinib should be used with caution in patients with mild or moderate renal impairment, but no dose reduction is necessary
- Dose reductions
 - Grade 3 or greater toxicities or intolerable grade 2 toxicities: temporary interrupt treatment until side effects recovered to grade 1 toxicity or less. Resume therapy at 40 mg once daily if necessary and at 20 mg once daily at a subsequent episode
 - Dose reductions are recommended for events that, if persistent, could become serious or intolerable.
- Missed dose
 - If there are still 12 hours or more before the next dose is due, then the missed dose should be taken as soon as possible. The next dose should be taken at the normal time.
 - If the next dose is due in less than 12 hours, then the missed dose should not be taken. The next dose should be taken at the normal time.
- Method of administration
 - Cabometyx is for oral use. The tablets should be swallowed whole and not crushed.
 - Patients should be instructed to not eat anything for at least 2 hours before through 1 hour after taking Cabometyx.\

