8.6 Replacement of individual subjects after withdrawal

If a participant decides to withdraw before start of treatment with Cabometyx, another patient will be recruited to replace this participant. If a participant withdraws after start of treatment, this patient will be regarded as 'lost to follow-up' and won't be replaced.

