10.2 Secondary study parameter(s)

- Assess the PFS
 - PFS will be estimated by a Kaplan-Meier curve
 - In SDC patients, PFS will be compared to PFS in AR-positive SDC patients which received ADT^{17,18} and HER2-positive SDC patients which received docetaxel plus trastuzumab.¹⁹
 - In ACC patients, PFS will be compared to PFS in ACC patients which received mitoxantrone monotherapy,^{20,21} vinorelbine monotherapy,²² epirubicin monotherapy,²³ or cisplatin plus anthracycline combination therapies²⁴
 - In other SGC patients, PFS will be described per individual case.
- Assess the OS
 - OS will be estimated by a Kaplan-Meier curve
 - In SDC patients, OS will be compared to a historical cohort of patients receiving best supportive care and a cohort receiving ADT.¹⁸
 - In ACC patients, median OS after disease recurrence is 6.4 years, and median OS after metastasis is 3.7 years.²⁵ OS of our study patients will be compared to these data and to OS data of phase II studies in ACC mentioned above (assess the PFS).
 - In other SGC patients, survival will be described per individual case
- Toxicity and QoL questionnaires will be described using simple descriptive statistics.
- Assess the response rate of patients with advanced SGC treated with cabozantinib by using continuous tumor shrinkage end-points, as was advocated by Billingham et al¹¹ and Wason et al.¹²
- Tumor shrinkage will be shown in a waterfall plot.

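### No quality-of-life form is planned when treatment stops for a reason other than progression, so QoL at the point of intolerance can go unrecorded

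*Combined protocol and SAP*

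**What the plan says.** QoL is a secondary objective in chapter 2: "Assess the QoL of patients treated with cabozantinib using EORTC questionnaires". Section 8.4 sets the timing, "Questionairres will be taken 7 times (at baseline, week 8, week 16, week 24, week 40, week 56 and at PD", and the questionnaire column of the chapter 3 table is marked at the same points. Neither place has an end-of-treatment row, and no questionnaire is marked at the visits in weeks 68, 80, 92 and 104.

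Under 5.1 treatment runs "until progressive disease, intolerable toxicity, or investigator and/or patient decision to withdraw for a maximum duration of 2 years". That is four ways to stop, of which only progression has a questionnaire attached.

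For patients who stop early, three places matter:

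- Section 8.4 lists the outpatient visits for a patient "if he/she is on treatment for the maximum duration of 2 years".
- Section 8.6 says: "If a participant withdraws after start of treatment, this patient will be regarded as 'lost to follow-up' and won't be replaced".
- Section 8.7 keeps everyone who took at least one dose in follow-up for 3 years, with PFS and OS as the stated purpose. QoL is not mentioned.

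The whole QoL analysis in 10.2 is one line: "Toxicity and QoL questionnaires will be described using simple descriptive statistics". There is no rule for missing forms, no completion rate and no breakdown by reason for stopping.

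**The concern.** The objective concerns the QoL of treated patients, and section 11.4 lists frequent reactions that patients feel directly: diarrhoea 74%, fatigue 56%, nausea 50%. A patient who stops because of such effects is informative for this objective, yet the plan schedules no form at that moment. Progression, by contrast, triggers one.

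Two things are at stake. The first is a missing measurement: QoL at intolerance may never be recorded. The second is conditional. If fixed-week forms end with treatment, the week 16, 24, 40 and 56 summaries describe a group that has progressively lost patients who could not tolerate the drug, and 10.2 has nothing to show the reader that this has happened. Cohorts are small (9 or 17), so one patient is 1/17 = 5.9% to 1/9 = 11.1% of a cohort.

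A separate coverage gap affects patients who stay on treatment: after week 56 only progression produces a form.

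**Working it through.** **1. The plan's own counts.** Fixed forms at weeks 0, 8, 16, 24, 40 and 56 make 6; adding progression gives 7, as stated in the summary and 8.4. The set has 30 + 35 + 3 + 1 = 69 questions, also as stated.

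**2. Reasons for stopping (5.1) against forms (chapter 3, 8.4).**

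| Treatment ends because of | Form planned at that event |
|---|---|
| Progression | Yes |
| Intolerable toxicity | No |
| Investigator or patient decision | No |
| 2-year cap (week 104) | No; last fixed form is week 56 |

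**3. What is on file when treatment stops without progression.** Intervals between fixed forms are 8, 8, 8, 16 and 16 weeks, then 104 − 56 = 48 weeks to the cap.

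| Stop (week) | Fixed post-baseline forms by then | Longest time since last fixed form |
|---|---|---|
| before 8 | 0 | just under 8 weeks (since baseline) |
| 8 to <16 | 1 | just under 8 weeks |
| 16 to <24 | 2 | just under 8 weeks |
| 24 to <40 | 3 | just under 16 weeks |
| 40 to <56 | 4 | just under 16 weeks |
| 56 to 104 | 5 | up to 48 weeks |

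Only a stop before week 8 leaves no scheduled on-treatment value after baseline. The other rows keep earlier forms, but none is tied to the stop.

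**4. Do fixed-week forms continue off treatment?** In 8.4 the on-treatment condition is attached to the visit list and the imaging list; the questionnaire list carries none. Section 8.6 points towards no further data, whereas 8.7 points towards continued follow-up, but for PFS and OS. The documents settle it neither way.

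**5. If they do continue.** The next fixed form could come almost 8 weeks after a stop before week 24, or almost 16 weeks after a stop between weeks 24 and 56. Section 13.1f gives a terminal half-life of about 120 hours, which is 5 days. Eight weeks is 56 / 5 = 11.2 half-lives, so such a form can be answered largely free of drug. A later form at progression also carries the effect of progression. Neither reliably records QoL at intolerance.

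**6. Effect of adding an end-of-treatment form.** Patients who stop at progression still have at most 7. Those who stop for another reason and progress later have at most 6 + 1 + 1 = 8. For 2-year completers the added form falls at the existing week 104 visit.

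**The case against.** Several points on the other side stand.

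- A reader might infer that patients who stop for toxicity fall out of the QoL objective. The documents do not support that. They keep their baseline form and every form completed before the stop, and 8.7 leaves a form at later progression possible.
- A reader might treat it as settled that fixed-week forms end with treatment. That is an inference from 8.4, 8.6 and 8.7. Section 8.6 may mean withdrawal from the study and 8.7 withdrawal from treatment, but the text does not draw that distinction.
- Patients who reach the 2-year cap are not those who tolerate the drug worst. The absence of a form after week 56 is a gap in coverage and is no evidence of a favourable bias.
- A reader might want a bias in score points. It would be the share of patients omitted times their score difference, and the documents give neither. The percentages in 11.4 are reaction rates of any grade, not stopping rates or QoL effects. An off-schedule form would also not enter the fixed-week means, so it would not by itself correct them.
- Tolerability is not undocumented: toxicity is scored at each post-baseline visit, and section 9 has adverse events recorded and followed. This does not replace the patient's own report.
- QoL is secondary and descriptive, and no stage 1 or final decision rule uses it. Seven administrations are stated consistently, so the schedule may be a deliberate limit on burden.

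These points narrow the concern. They do not explain why progression alone among the ways of stopping has a form, or why 10.2 is silent on missing forms.

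**Conclusion.** The gap is real and limited. As written, three of the four ways of ending treatment have no QoL assessment attached, so QoL at intolerance can go unrecorded; for a stop before week 8, no on-treatment value after baseline is scheduled at all. That later summaries lean towards patients who tolerate the drug rests on two assumptions: that fixed-week forms end with treatment, which the plan leaves open, and that patients who stop have worse QoL, which is plausible when the reason is intolerable toxicity. The number of patients affected and the size of any bias cannot be computed, because no stopping rate is given. The absence of fixed forms between week 56 and week 104 is a separate gap of 48 weeks and four visits. The primary endpoint, sample size and error rates are untouched. The change is worth making because it is cheap and improves a stated secondary objective.

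**What to change.** - In the chapter 3 table and 8.4, replace the progression-only questionnaire with one at end of treatment for any reason, and at progression if that comes later. For 2-year completers this is the existing week 104 visit. Bring the count in the summary into line.
- State whether the fixed-week forms continue after treatment stops.
- Reconcile 8.6 with 8.7, so that it is clear which patients are lost to follow-up and what is still collected from the others.
- In 10.2, report questionnaire completion by time point and reason for stopping, and change from baseline to the end-of-treatment form next to the per-visit summaries. The completion table lets a reader judge selection in the fixed-week means, which the added form alone does not correct.

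The cost is at most one extra 69-question set per patient (a maximum of 8 instead of 7), updated patient-information wording, and no extra staff.
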